8.1.2.2 Tumor Response Evaluation

After induction chemotherapy: Response evaluation after induction chemotherapy and restaging before study intervention with peposertib and CRT are provided in [Appendix 5](#). The evaluation with MRI, endoscopy, and DRE is to be done before starting treatment/randomization (peposertib and CRT). Overall response is evaluated as progressive disease, stable disease, partial response, nearly complete response, or complete response. Participants who present with stable disease, partial response, or nearly complete response may enter the study, participants who present with tumor progression or cCR should be treated according to standard practice per institutional guidelines.

After peposertib and CRT: Response evaluation criteria after treatment and restaging before surgery are provided in [Appendix 5](#). The evaluation with MRI, endoscopy, and DRE is to be done at Week 14 (± 7 days). Overall response is evaluated as progressive disease, incomplete response, nearly complete response, or complete response.

During Long-term Safety Follow-up: Response evaluation is provided in [Appendix 5](#).

If a scan shows progressive disease, it will be indicated whether it is local recurrence, distant recurrence, or both.

Tumor assessments are performed until progressive disease or the participant withdrawal of consent. Tumor assessments will be stopped on subsequent start of new anticancer therapy, with the exception of starting adjuvant treatment described in [Section 6.5](#).

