9.4.1 Efficacy Analyses

Statistical analysis methods for efficacy endpoints are described in [Table 12](#).

Table 12 Statistical Analysis Methods for Efficacy Endpoints

Endpoint	Statistical Analysis Methods
Secondary	
Composite endpoint of pCR/cCR	Derivation of the pCR/cCR composite endpoint (pCR based on local review) is described in Section 3.1 . The proportion of participants with pCR/cCR is indicated together with the 95%-Clopper-Pearson CI. The analysis will be performed on the FAS.
Disease-Free Survival	Disease-free Survival time, defined as the time from first treatment day to the date of the first documentation of objective progressive disease or death due to any cause, whichever occurs first. The analysis will be performed as described below for time-to-event endpoints.
pCR	The definition of pCR is provided in Section 3.1 . pCR will be analyzed once on the local review of the histology slides. The proportion of participants with pCR will be reported together with the corresponding 95% CIs. The analysis will be performed on the FAS

Endpoint	Statistical Analysis Methods
cCR	The definition of cCR is provided in Section 3.1. The proportion of participants with cCR will be reported together with the corresponding 95% CIs. The analysis will be performed on the FAS
Local/distant recurrence	The following analyses will be performed: 
 • Time from surgery to local recurrence • Time from surgery to distant recurrence. The analyses will be performed as described below for time-to-event endpoints.
Neoadjuvant Rectal Score	The neoadjuvant rectal score will be presented in terms of summary statistics (such as mean, median, standard deviation, and quartiles) and graphically. The analysis will be performed on the FAS Population.

cCR=Clinical Complete Response, CI=confidence interval, CR=complete response, FAS=Full Analysis Set, pCR=Pathological Complete Response.

In addition to analyses specified in [Table 12](#), for the primary and main secondary endpoints subgroup analyses on baseline variables such as gender, tumor stage, etc. will be performed.

Analysis of Time-to-event Endpoints

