Appendix 6 Pathology Assessments

- **Grading of quality and completeness of the mesorectum in a TME**

	Mesorectum	Defects	Coning	CRM
Complete	Intact, smooth	Not deeper than 5 mm	None	Smooth, regular
Nearly complete	Moderate bulk, irregular	No visible muscularis propria	Moderate	Irregular
Incomplete	Little bulk	Down to the muscularis propria	Moderate/ marked	Irregular

- **Definition of surgical margin status**

- Margin Type

Proximal margins	The proximal surgical margin refers to the most cephalad portion of the specimen (i.e. closest to participants's head)
Distal margins	The distal margin refers to the most caudad portion (i.e. closest to participant's anus)
Radial margins	The radial margin, synonymously termed circumferential margin refers to the outer circumference of the rectal specimen

- Margin positivity

Positive	A surgical margin is positive if the pathologist notes tumor within ≤ 1 mm of any edge of the primary tumor specimen
Close	A surgical margin is close if the pathologist notes tumor > 1 but ≤ 3 mm of any edge of the primary tumor specimen
Negative	A surgical margin is negative if the pathologist notes there is no tumor within 3 mm of any edge of the primary tumor specimen

- **Overall completeness of TME resection**

- The AJCC 8th edition will be used to categorize the completeness of the TME resection.

R0 resection	All gross disease has been removed and microscopic examination reveals all surgical margins free of tumor. This must include the proximal, distal, and radial margin. Tumor > 1 mm from the tumor resection margins is considered R0.
R1 resection	There is evidence of tumor cells at 1 or more surgical resection margin based on microscopic pathologic assessment of the tumor specimen but there is no macroscopic evidence of tumor at any resection margin nor is there macroscopic evidence of residual tumor based on the surgeon's operative report
R2 resection	The surgical pathologist identifies any macroscopic evidence of tumor at any of the surgical resection margins or there is macroscopic evidence of residual tumor based on the surgeon's operative report
No resection	Removal of the primary tumor was not performed

- Pathology TNM staging: After TME resection, participants will be staged according to AJCC 8th edition.

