 - T describes how far the main (primary) tumor has grown into the wall of the intestine and whether it has grown into nearby organs. Because this information will be ascertained from the surgical pathology report it is denoted with a prefix “p”. Because it is ascertained after neoadjuvant treatment, the prefix “y” is also added (i.e. ypTx).

Tx	Primary tumor cannot be assessed
T0	No evidence of primary tumor
Tis	Carcinoma in situ, intramucosal carcinoma (involvement of lamina propria with no extension through muscularis mucosae)
T1	Tumor invades the submucosa (through the muscularis mucosa but not into the muscularis propria)
T2	Tumor invades the muscularis propria
T3	Tumor invades through the muscularis propria into pericolorectal tissues
T4a	Tumor invades the visceral peritoneum (including gross perforation of the bowel through tumor and continuous invasion of tumor through area of inflammation to the surface of the visceral peritoneum)
T4b	Tumor directly invades or adheres to adjacent organ or structures

- N describes the extent of spread to nearby (regional) lymph nodes based on rectal resection specimen. The prefix “yp” is added as described above.

Nx	Regional lymph nodes cannot be assessed
N0	No regional lymph node metastasis
N1a	1 regional lymph node is positive
N1b	2 or 3 regional lymph nodes are positive.
N1c	No regional lymph nodes are positive, but there are tumor deposits in the: 
 • Subserosa • Mesentary • Non-peritonealized pericolic, or perirectal/ mesorectal tissues
N2a	4 to 6 regional lymph nodes are positive.
N2b	7 or more regional lymph nodes are positive.

- M describes the extent of spread to distant sites outside the pelvis

M0	No distant metastasis outside the pelvis
M1a	Metastasis to 1 site or organ is identified without peritoneal metastasis
M1b	Metastasis to 2 or more sites or organs is identified without peritoneal metastasis
M1c	Metastasis to the peritoneal surface is identified alone or with other site or organ metastasis

▪ Pathologic AJCC 8th Edition staging summary

When T is...	and N is...	and M is...	Stage group is
Tis	N0	M0	0
T1, T2	N0	M0	I
T3	N0	M0	IIA
T4a	N0	M0	IIB
T4b	N0	M0	IIC
T1-T2	N1/N1c	M0	IIIA
T1	N2a	M0	IIIA
T3-T4a	N1/N1c	M0	IIIB
T2-T3	N2a	M0	IIIB
T1-T2b	N2b	M0	IIIB
T4a	N2a	M0	IIIC
T3-T4a	N2b	M0	IIIC
T4b	N1-N2	M0	IIIC
Any T	Any N	M1a	IVa
Any T	Any N	M1b	IVb
Any T	Any N	M1c	IVc

• Degree of pathological treatment response

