For identification of previous or concomitant medications/procedures, no formal imputation will be performed on missing or incomplete dates. Table 3 indicates whether a treatment is considered to be stopped before or after start of treatment. Rules presented in [Table 4](#) will be used to define if a medication/procedure is considered as a previous, concomitant or both previous and concomitant medication/procedure.

Table 3 Stopping rules for medication/procedure end dates

End date of medication/procedure			Stopping rule
Day	Month	Year	
UNK	UNK	UNK	After treatment start (ongoing)
UNK	UNK	< Treatment start (year)	Before treatment start
UNK	UNK	>= Treatment start (year)	After treatment start
		< Treatment start (month and year)	Before treatment start
		>= Treatment start (month and year)	After treatment start
		< Treatment start (complete date)	Before treatment start
		>= Treatment start (complete date)	After treatment start

UNK = Unknown

Table 4 Rules to define previous and/or concomitant medications

Start date of medication/procedure			Stopping rule (see Table 3)	Medication/ procedure
Day	Month	Year		
UNK	UNK	UNK	Before treatment start	Previous
UNK	UNK	UNK	After treatment start	Previous and concomitant
UNK	UNK	<= Treatment start (year)	Before treatment start	Previous
UNK	UNK	<= Treatment start (year)	After treatment start	Previous and concomitant
UNK	UNK	> Treatment start (year) and <= Treatment end + 30 days (year)	After treatment start	Concomitant
UNK		<= Treatment start (month and year)	Before treatment start	Previous
UNK		<= Treatment start (month and year)	After treatment start	Previous and concomitant
UNK		> Treatment start (month and year) and <= Treatment end + 30 days (month and year)	After treatment start	Concomitant
		<= Treatment start (date)	Before treatment start	Previous
		<= Treatment start (date)	After treatment start	Previous and concomitant
		> Treatment start (date) and <= Treatment end + 30 days (date)	After treatment start	Concomitant

UNK = Unknown

Tumor assessments

Tumor response assessments will be based on MRI, endoscopic and digital rectal evaluation (DRE). All investigation dates (e.g. MRI, endoscopy, DRE) must be completed with day, month and year.

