Tumor assessments during the long-term safety and survival follow-up period will be sorted by dose level, subject identification number and assessment visit and listed with the following variables:

- Dose level
- Subject identification number
- Assessment visit
- Date of imaging
- Assessment method
- Overall status.

Finally, all information available on the “RECTAL SURGERY AT WEEK 15” eCRF page will be listed. The listing will be sorted by dose level, subject identification number and date of surgery and will display the following variables:

- Dose level

- Subject identification number
- Date of surgery
- Surgery procedure
- Outcome of surgery
- Histological response.

14.2

Secondary Endpoint: Disease-Free Survival

Population: FAS analysis set

Disease-free survival (DFS) time is defined as the time from the first treatment day to the date of the first documentation of objective progression of disease (PD) or death due to any cause, whichever occurs first. DFS data will be censored on the date of the last adequate tumor assessment for participants who do not have an event (PD or death) or for participants with an event after two or more subsequent missing tumor assessments (i.e. 2 times the scheduled time interval between two subsequent response assessments). Participants who do not have a baseline tumor assessment or who do not have any post baseline tumor assessments will be censored at the start of first trial treatment unless death occurred on or before the time of the second planned tumor assessment, in which case the death will be considered an event.

The last adequate tumor assessment is defined as the last tumor assessment result that is not “NE” or “NA”.

Disease-free survival in months is calculated as follows:

$$\text{DFS (months)} = [\text{date of event or censoring} - \text{treatment start date} + 1]/30.4375$$

Table 6 Date of event / censoring for DFS analysis

Status		Censoring	Date of event / censoring
Progressed or died	No consecutive missing tumor assessments	Event	Minimum (Date of PD, Date of death)
	After two or more subsequent missing tumor assessments (i.e. 2 times the scheduled time interval between two subsequent response assessments)	Censored	Date of last tumor assessment with outcome CR, Nearly-CR or IR or treatment day 1, whatever is later

Neither progressed nor died and no missed tumor assessment	Censored	Date of last tumor assessment with outcome CR, Nearly-CR or IR or treatment day 1 whatever is later

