14.3 Secondary Endpoint: Local Recurrence and/or Distant Metastasis

Population: FAS analysis set (participants with surgery only)

Time from surgery to local recurrence will be defined as time from day of surgery to the date of the first documentation of progression of disease, flagged as 'local recurrence' or 'local recurrence and distant metastasis' ('TUMOR ASSESSMENT(ACCORDING TO NCCN) DURING LONG-TERM SAFETY AND SURVIVAL FOLLOW-UP' eCRF page).

Time from surgery to distant metastasis will be defined as time from day of surgery to the date of the first documentation of progression of disease, flagged as 'distant metastasis' or 'local recurrence and distant metastasis' ('TUMOR ASSESSMENT(ACCORDING TO NCCN) DURING LONG-TERM SAFETY AND SURVIVAL FOLLOW-UP' eCRF page). Only subjects who undergo rectal surgery (week 15) will be included in this analysis.

Table 8 Date of event / censoring definition for Local/Distant recurrence Analysis

	Status	Censoring	Date of event / censoring
Time to local recurrence: PD flagged as 'Local recurrence' or 'Local recurrence and distant metastasis'	No consecutive missing tumor assessments	Event	Date of progression
	After two or more subsequent missing tumor assessments (i.e. 2 times the scheduled time interval between two subsequent response assessments)	Censored	Date of last tumor assessment with outcome CR or date of surgery, whatever is later
Time to distant metastasis: PD flagged as 'Distant metastasis' or 'Local recurrence and distant metastasis'	Time to local recurrence: No consecutive missing tumor assessments and PD flagged as 'Distant metastasis'	Censored	Date of progression
	Time to distant metastasis: No consecutive missing tumor assessments and PD flagged as 'Local recurrence'		
No PD flagged as 'Local recurrence', 'Distant metastasis' or 'Local Recurrence and Distant metastasis' and no missed tumor assessment		Censored	Date of last tumor assessment with outcome CR or date of surgery, whatever is later

CR = Complete response; PD = Progressive disease

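### The recurrence and DFS rules have no proper place for residual tumor (R2) or metastasis found at the Week 15 operation

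*Protocol*

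**What the plan says.** Protocol Appendix 6 sorts each operation into R0, R1, R2 or no resection. R2 applies when "The surgical pathologist identifies any macroscopic evidence of tumor at any of the surgical resection margins or there is macroscopic evidence of residual tumor" (the sentence goes on to name the operative report). The same appendix stages distant spread from M0 to M1c; M1c, for example, is "Metastasis to the peritoneal surface is identified alone or with other site or organ metastasis". Protocol 8.1.1 requires all surgical and pathology reports for the resection to be submitted. SAP 14.1 tabulates and lists the outcome of surgery and tabulates ypTNM.

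The time-to-event rules are built from other data:

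- **DFS** (Protocol Table 12; SAP 14.2) ends at "the date of the first documentation of objective progression of disease (PD) or death due to any cause". SAP Section 9 bases tumor response on MRI, endoscopy and digital rectal examination. Table 6 censors at the last assessment showing complete, nearly complete or incomplete response.
- **Recurrence** (SAP 14.3, Table 8) is the "time from day of surgery to the date of the first documentation of progression of disease" carrying a local or distant flag on the long-term follow-up page. On who enters, the SAP says: "Only subjects who undergo rectal surgery (week 15) will be included in this analysis". There is no condition on resection status. Without a flagged progression, the participant is censored at the later of the last complete-response assessment and the date of surgery.
- **Flagging** depends on imaging. Protocol 8.1.2.2 says: "If a scan shows progressive disease, it will be indicated whether it is local recurrence, distant recurrence, or both". Table 17 in Appendix 5 has two outcomes for this period: progression, meaning local or distant recurrence, and complete response.

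**The concern.** A tumor that was not fully removed cannot recur, yet the local-recurrence analysis admits the participant and can record the remnant only as recurrence or not at all. A metastasis seen at operation is direct evidence of distant disease, yet it has no route into the distant-metastasis endpoint.

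The schedule makes the second gap more than formal. Chest-abdominal CT is described only before treatment (Protocol Section 8). Week 14 restaging is MRI, endoscopy and rectal examination, and Table 16 has no category for distant disease. No scan is done at Week 21. The operation may therefore be the first look at distant sites since baseline.

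At stake are the meaning of the local-recurrence curve, the completeness of the distant-metastasis curve, and the dating and censoring of DFS events, in a study where one participant moves an estimate by about five points.

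**Working it through.** The plan gives no expected rate or event target for DFS or recurrence, so there is no figure of its own to reproduce. The check has three steps.

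**1. Trace each finding through the rules.**

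| Finding at Week 15 | What follows | Recurrence (Table 8) | DFS (Table 6) |
|---|---|---|---|
| R2 | scored as progression at Week 27 | local recurrence, dated Week 27 | event, dated Week 27 |
| R2 | scans stop for new therapy | censored at surgery | censored at Week 14 assessment |
| M1, not removed | scored as progression at Week 27 | distant metastasis, dated Week 27 | event, dated Week 27 |
| M1, removed | later scans clear | never an event | never an event unless scored as progression by some route the SAP does not describe |
| No resection | – | not stated whether this counts as surgery | no rule |

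The second row follows from Protocol 8.1.2.2, under which tumor assessments stop when new anticancer therapy other than the permitted adjuvant treatment begins.

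**2. Delay.** Surgery is at Week 15 ± 2 and the first later scan at Week 27 ± 2. Nominal gap: 27 − 15 = 12 weeks. Shortest: 25 − 17 = 8. Longest: 29 − 13 = 16.

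**3. Size for DFS.** Kaplan-Meier, S(t) = Π(1 − d/n). N = 19 is the number treated by 06 May 2021 (Protocol Synopsis). Assumptions: one affected participant, two other progressions at Week 39, everyone else censored at Week 52.

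- Finding counted on the surgery date: Week 26, 18/19 = 94.7%; Week 52, 18/19 × 16/18 = 84.2%.
- Flagged at Week 27: Week 26, 100%; Week 52, 18/19 × 16/18 = 84.2%. Only the date differs.
- Scans stopped, censored at Week 14: Week 52, 16/18 = 88.9%, which is 4.7 points higher.
- Never flagged: Week 52, 17/19 = 89.5%, which is 5.3 points higher.

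With two affected participants the surgery-date value is 15/19 = 78.9%, against 15/17 = 88.2% (censored) and 17/19 = 89.5% (never flagged). With three it is 14/19 = 73.7%, against 14/16 = 87.5% and 89.5%. For N from 18 to 30 and one to three affected, the difference in the last two scenarios runs from about 3 points (N = 30, one censored: 93.1 − 90.0) to about 17 (N = 18, three never flagged: 88.9 − 72.2).

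**Local recurrence** at 37 weeks after surgery (52 − 15), with all 19 operated on and both other events taken as local: one R2 remnant counted as recurrence gives 16/19 = 84.2%; leaving that participant out gives 16/18 = 88.9%. Here the present rule makes the result look worse, not better. Censoring at surgery also gives 88.9%, but the persistent disease then disappears from this endpoint.

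**The case against.** The strongest reply concerns what this DFS is. Its clock starts on the first treatment day with tumor in place, and Table 6 accepts incomplete response as event-free. It behaves like progression-free survival for everyone. A remnant that has not grown is not progression, so making R2 an event redefines the protocol endpoint. It would also do so unevenly, because an unoperated participant with visible tumor would stay event-free. This stands, and is why R2 belongs in an added DFS analysis and not in the main one.

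Other points also stand:

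- Nothing expressly bars an operative or histological metastasis from being objective progression; the case is unspecified. Programmers still have no rule or data route for it.
- Stage II/III is at original staging, so M1 at surgery may have been occult at entry. That does not affect when it was first documented.
- The endpoints are secondary, in an exploratory single-arm study without hypothesis tests. Outcome of surgery is tabulated and listed, so R2 cases stay visible if that field holds the R class, which the SAP does not say.
- Data from 16 of 19 participants up to Week 19 were already available, open-label, so a change now is made with knowledge of the data.

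A reader might infer that these participants always remain at risk of recurrence. They do not: Table 8 censors at surgery unless a later assessment shows complete response. A reader might also infer that 1-year DFS is always overstated. It is not: progression scored at Week 27 leaves it unchanged. One participant in a cohort of three suggests a 33-point shift per dose level, but SAP Tables 7 and 9 present Kaplan-Meier estimates overall only.

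**Conclusion.** The point holds for the recurrence endpoints as a fault in a stated rule. Table 8 mixes persistent tumor with recurrence, or censors it at surgery, and does not count a metastasis found at operation. For DFS it holds as a missing rule: R2 and M1 at surgery may be dated 8 to 16 weeks late, censored or missed. The documents do not support saying that an abandoned resection is admitted to the SAP 14.3 analysis; they leave that undefined.

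The size depends on what happens after surgery. One affected participant among 19, with two other events, moves Week 52 DFS by 0, 4.7 or 5.3 points. The number affected and the number of other events are assumptions, and the documents give no frequency of R2, no resection or M1 at surgery. The consequence is limited to exploratory secondary endpoints, but the correction is cheap.

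**What to change.** - **SAP 14.3, Table 8.** Limit time to local recurrence to R0 and R1 resections. Report R2 and no resection separately as persistent disease. Count M1 documented at surgery as a distant-metastasis event on the surgery date. State whether the existing rule that censors local recurrence on the date of a distant-only progression then applies to these participants.
- **SAP 14.2, Table 6.** Count M1 documented at surgery as a DFS event on the surgery date. Add an analysis in which R2, or an operation that leaves the primary unresected, is also an event on that date. Participants not operated on, including those with clinical complete response, are unaffected. Keep the PD-or-death version alongside.
- **SAP Section 7.** Declare the change and say that it was made after most participants had passed Week 19.

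Cost: revised SAP wording and a small derivation. The surgical and pathology reports are already required, but the R class, or the reason for no resection, may have to be read from them if the outcome-of-surgery field does not hold it, and ypTNM may not exist where nothing was resected. DFS and distant-metastasis estimates may become slightly less favorable.
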